In case of evidence of TLS, dosing with venetoclax should be interrupted and/or reduced (refer to [Appendix F](#)). Drug interruption for up to 72 hours following transient (i.e., lasting < 48 hours) chemical changes and laboratory TLS will not require a dose reduction. If the TLS has not resolved within 72 hours, then a dose reduction should be considered. The subject may be allowed to re-escalate to the final dose based on a risk assessment (including tumor burden status) after discussion between the investigator and the TA MD. If active correction of electrolytes was performed, the first dose of venetoclax should only be given when electrolytes have been stable without additional treatment for at least 24 hours. For subjects who have had a dosing interruption lasting more than 1 week during the ramp-up or more than 2 weeks when subjects are receiving the daily dose of 400/600 mg, TLS risk should be reassessed to determine if restarting at a reduced dose is necessary (e.g., all or some levels of the dose titration).

Management of Treatment-Related Neutropenia

Complete blood counts should be monitored throughout the treatment period. Dose interruptions are required and dose reductions might be needed for subjects with severe neutropenia. Supportive measures including antimicrobials for any signs of infection and prophylactic use of growth factors (e.g., granulocyte-colony stimulating factor [G-CSF]) should be considered (refer to [Appendix F](#)).

Prophylaxis for Infection

Anti-infective prophylaxis for viral (e.g., acyclovir, zelitrex, or similar agent) and/or bacterial (e.g., trimethoprim-sulfamethoxazole and either levofloxacin or amoxicillin-clavulanate or similar agents

and pneumococcal vaccination) infections is required for all subjects with ANC of $< 500/\mu\text{L}$ at any time point. Institutional infectious organisms and their drug resistance patterns should primarily be considered and the choice of these agents should be based on regional guidelines or institutional standards. The investigator should confirm that the prophylaxis agent(s) can be safely administered with study drugs. Some medications may require dose adjustments due to the potential for drug-drug interactions. Refer to [Table 4](#) and [Table 5](#) for implementing dose modifications for venetoclax + ibrutinib as necessary.

Management of Infection

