Dose reduction Level 3	Discontinue

For dose modification during concomitant treatment with CYP3A inhibitors, refer to [Table 1](#).

During combination dosing with venetoclax, the decision to dose modify a study drug due to a toxicity will be based on the investigator attribution of relatedness to a given drug. For example, if an AE occurs and is considered related to venetoclax but not ibrutinib, the dose of venetoclax should be modified while ibrutinib should remain the same. If the AE is considered potentially related to both drugs, adjusting the dose of venetoclax before ibrutinib is the recommended first action, taking into consideration the possibility of higher systemic exposure of venetoclax when administered in combination with ibrutinib. For cases where the investigator is uncertain of what action to take, the TA MD may be contacted for further discussion.

If ibrutinib is discontinued for toxicity, then treatment with venetoclax may be continued.

Please consult the ibrutinib Investigator's Brochure⁹ for more details regarding management of known risks of the drug and/or discontinuation (permanent or temporary).

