APPENDIX D. DEFINITIONS OF LABORATORY AND CLINICAL TUMOR LYSIS SYNDROME

Metabolic Abnormality	Criteria for Classification of Laboratory Tumor Lysis Syndrome	Criteria for Classification of Clinical Tumor Lysis Syndrome
Hyperuricemia	Uric acid > 8.0 mg/dL (475.8 μmol/L) in adults or above the upper limit of the normal range for age in children	
Hyperphosphatemia	Phosphorus > 4.5 mg/dL (1.5 mmol/L) in adults or > 6.5 mg/dL (2.1 mmol/L) in children	
Hyperkalemia	Potassium > 6.0 mmol/liter	Cardiac dysrhythmia or sudden death probably or definitely caused by hyperkalemia
Hypocalcemia	Corrected calcium < 7.0 mg/dL (1.75 mmol/L) or ionized calcium < 1.12 mg/dL (0.3 mmol/L) ^a	Cardiac dysrhythmia, sudden death, seizure, neuromuscular irritability (tetany, paresthesias, muscle twitching, carpopedal spasm, Trousseau's sign, Chvostek's sign, laryngospasm, or bronchospasm), hypotension, or heart failure probably or definitely caused by hypocalcemia
Acute kidney injury ^b	Not applicable	Increase in the serum creatinine level of 0.3 mg/dL (26.5 μmol/L) (or a single value > 1.5 × the upper limit of the age-appropriate normal range if no baseline creatinine measurement is available) or the presence of oliguria, defined as an average urine output < 0.5 mL/kg/hr for 6 hrs

a. The corrected calcium level in mg/dL = measured calcium level in mg/dL + 0.8 × (4-albumin in g/dL).

b. Acute kidney injury is defined as an increase in the creatinine level of at least 0.3 mg/dL (26.5 μmol/L) or a period of oliguria lasting 6 hours or more. By definition, if acute kidney injury is present, the subject has clinical tumor lysis syndrome.

Note: In laboratory tumor lysis syndrome, 2 or more metabolic abnormalities must be present during the same 24-hour period within 3 days before the start of therapy or up to 7 afterward. Clinical tumor lysis syndrome requires the presence of laboratory tumor lysis syndrome plus an increased creatinine level, seizures, cardiac dysrhythmia, or death.

Source: Howard SC, Jones DP, Pui CH. The tumor lysis syndrome. *N Engl J Med.* 2011;364(19):1844-54.

APPENDIX E. RECOMMENDATIONS FOR INITIAL MANAGEMENT OF ELECTROLYTE ABNORMALITIES AND PREVENTION OF TUMOR LYSIS SYNDROME

Abnormality	Management Recommendations
Hyperkalemia (Including Rapidly Rising Potassium)	

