APPENDIX F. RECOMMENDED DOSE REDUCTIONS RELATED TO DRUG TOXICITIES

Recommended Venetoclax Dose Modifications for Toxicities

Event	Occurrence	Action
Tumor Lysis Syndrome		
Blood chemistry changes or symptoms suggestive of TLS	Any	Withhold the next day's dose. If resolved within 24 to 48 hours of last dose, resume at the same dose.
		For any blood chemistry changes requiring more than 48 hours to resolve, resume at a reduced dose (see Table 4).
		For any events of clinical TLS, resume at a reduced dose following resolution (see Table 4).
		Dose reduction or interruption of companion study drug may occur at the discretion of the investigator.
Non-Hematologic Toxicities		
Grade 3 or 4 non-hematologic toxicities	1 st occurrence	Interrupt venetoclax. Once the toxicity has resolved to Grade 1 or baseline level, venetoclax therapy may be resumed at the same dose. No dose modification is required.
	2 nd and subsequent occurrences	Interrupt venetoclax. Follow dose reduction guidelines in Table 4 when resuming treatment with venetoclax after resolution. A greater dose reduction may occur at the discretion of the investigator.
Hematologic Toxicities		
Grade 3 or 4 neutropenia with infection or fever; or Grade 4 hematologic toxicities (except lymphopenia)	1 st occurrence	Interrupt venetoclax. To reduce the infection risks associated with neutropenia, G-CSF may be administered with venetoclax if clinically indicated. Once the toxicity has resolved to Grade 1 or baseline level, venetoclax therapy may be resumed at the same dose.
	2 nd and subsequent occurrence	Interrupt venetoclax. Consider using G-CSF as clinically indicated. Follow dose reduction guidelines in Table 4 when resuming treatment with venetoclax after resolution. Additional dose reductions may occur at the discretion of the physician.
Consider discontinuing venetoclax for subjects who require dose reductions to less than 100 mg for more than 2 weeks.		

G-CSF = granulocyte-colony stimulating factor; TLS = tumor lysis syndrome

Recommended Ibrutinib Dose Modifications for Toxicities

Event	Occurrence	Action

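### Section 6.2 and Appendix F of the protocol give different restart-dose rules for venetoclax after tumor lysis syndrome, and neither says which governs

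*Protocol*

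**What the plan says.** The restart dose after TLS is addressed in Protocol Section 6.2 (Prophylaxis and Management of Tumor Lysis Syndrome) and again in the venetoclax table of Appendix F.

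The Section 6.2 paragraph opens with a general instruction, without a time limit, to interrupt venetoclax, reduce it, or both when there is evidence of TLS, and it refers to Appendix F. It then exempts short events. For changes described as transient, meaning under 48 hours, an interruption of up to 72 hours after such "chemical changes and laboratory TLS will not require a dose reduction". Next comes its only timed trigger for a reduction: "If the TLS has not resolved within 72 hours, then a dose reduction should be considered".

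Appendix F has three rules:
- Short events: "If resolved within 24 to 48 hours of last dose, resume at the same dose".
- Longer events: "For any blood chemistry changes requiring more than 48 hours to resolve, resume at a reduced dose", with a reference to Table 4.
- Clinical TLS of any duration: "For any events of clinical TLS, resume at a reduced dose following resolution", again by Table 4.

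Section 6.2 also tells the investigator what to do when in doubt about a dose change: "For cases where the investigator is uncertain of what action to take, the TA MD may be contacted for further discussion".

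**The concern.** The two texts use different times (72 and 48 hours) and verbs of different strength (a reduction to be considered, against an instruction to resume lower). Appendix F singles out clinical TLS; Section 6.2 does not. An investigator who acts on the timed sentences in Section 6.2 and one who acts on Appendix F can restart the same subject at different doses, each following the protocol.

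TLS is an adverse event of special interest (Section 6.1). Because of the short ramp-up, every subject is managed as high risk (Section 6.2). A restart that is too high re-exposes a subject who has just had the event. One that is lower than necessary withholds dose in an aggressive leukemia. The choice should not depend on which page was read.

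**Working it through.** No sample size, error rate or event count is involved, so the check compares the texts case by case and then sizes one dose step.

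**Comparison by time to resolution and type of event**

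| Event | Section 6.2 | Appendix F | Possible difference |
|---|---|---|---|
| Laboratory changes only, resolved in under 48 h | No reduction required | Same dose | None |
| Laboratory changes, resolved after 48 h and by 72 h | No timed rule; only the general instruction and the pointer to Appendix F | Reduced dose | 0 to 1 step |
| Laboratory changes, not resolved by 72 h | Reduction to be considered | Reduced dose | 0 to 1 step |
| Clinical TLS, any duration | No separate rule; the 72-hour sentence speaks of TLS in general | Reduced dose | 0 to 1 step |

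The second row is a gap in Section 6.2 set against a rule in Appendix F. The exemption in Section 6.2 ends at 48 hours and its trigger starts at 72 hours. In the third row both texts speak and differ in force.

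The exemption sentence is also loosely built. The 48-hour limit stands in front of the chemical changes, and laboratory TLS follows after the conjunction. The natural reading applies the limit to both, and the table uses that reading. A hurried reader could apply it to the chemical changes alone.

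**Size of one step**

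Inputs: Table 4 in Section 6.2. Formula: (dose at interruption − restart dose) / dose at interruption.

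- 600 to 400 mg: 200/600 = 33%
- 400 to 300 mg: 100/400 = 25%
- 300 to 200 mg: 100/300 = 33%
- 200 to 100 mg: 100/200 = 50%
- 100 to 50 mg: 50/100 = 50%
- 50 to 20 mg: 30/50 = 60%
- 20 to 10 mg: 10/20 = 50%

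One step is therefore 25% to 60% of the daily dose: 25% at the 400 mg target and 60% at 50 mg. Under footnote a of Table 4, a subject who is not in hospital stays on the reduced dose for 1 week before an increase.

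**Effect on the analysis**

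SAP Section 7.2 identifies TLS by a narrow standardized MedDRA query, and SAP Section 7.3 by four laboratory analytes. Neither uses the restart rule. The SAP table of adverse events leading to venetoclax reduction will record whatever each site did, but its definition is unaffected.

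**The case against.** The best defense is that Appendix F governs in practice. Section 6.2 refers to it three times: in the introductory TLS paragraph, which says that reductions may be needed; in the first sentence of the paragraph at issue; and under dose modifications for venetoclax. A reader of Section 6.2 is sent to Appendix F before reaching the 72-hour sentence. Appendix F is itself headed as recommended, and the sponsor's medical director can be consulted.

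Much of this stands. It rules out two stronger readings that a reader might infer:
- *That Section 6.2 permits a reduction only after 72 hours.* It does not say so. Its general instruction to interrupt, reduce, or both has no time limit.
- *That Section 6.2 prescribes the same dose from 48 to 72 hours.* It is silent there, so the difference is zero to one step and not a fixed step.

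The cross-references do not remove the conflict. After the pointer, Section 6.2 states a different time and verb, and nothing says which text prevails. Two recommendations with different thresholds still yield different doses. Consultation helps only an investigator who notices the discrepancy.

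Two further inferences should be avoided. First, the missed doses cannot simply be counted. Section 6.2 also asks for 24 hours of stable electrolytes without further treatment before dosing if they were actively corrected. If that applies to restarts, 48 + 24 = 72 hours, which may be why a 72-hour interruption is tolerated after a change lasting under 48 hours. It does not explain the next sentence, which concerns TLS still unresolved at 72 hours.

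Second, a reader might infer that Appendix D contradicts itself on clinical TLS. Footnote b says "By definition, if acute kidney injury is present, the subject has clinical tumor lysis syndrome", while the Note says "Clinical tumor lysis syndrome requires the presence of laboratory tumor lysis syndrome plus an increased creatinine level, seizures, cardiac dysrhythmia, or death". Taken separately, the two sentences classify kidney injury without laboratory TLS differently. They can be read together, with the Note giving the general requirement and the footnote naming a qualifying event. The table is attributed to a published source that is not available here. Footnote b also gives the cautious result, a reduced dose, which a rewording could remove. The documents do not make a case for changing Appendix D.

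**Conclusion.** The inconsistency is real and limited. Section 6.2 and Appendix F agree for laboratory changes resolved in under 48 hours. Beyond that, and for clinical TLS, Appendix F reduces the dose, while Section 6.2 either gives no specific rule or leaves the reduction optional. The restart dose can differ by zero to one Table 4 step, or up to 25% to 60% of the daily dose depending on the level.

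This assumes that both texts measure the same duration. Appendix F counts its same-dose window from the last dose; Section 6.2 does not say when its clock starts. It also assumes a reduction of one step, although Section 6.2 and Appendix F leave room for judgment. The documents give no frequency for these events, so no expected number of affected subjects can be stated.

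The matter concerns subject safety and consistency between sites. Prophylaxis and laboratory monitoring do not depend on either restart rule, and sample size, error rates and the response-rate analysis are untouched. It is worth correcting because the correction is cheap.

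**What to change.** Edit two sentences in Section 6.2:

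1. Replace the 72-hour sentence with: *If blood chemistry changes take more than 48 hours to resolve, or after any clinical TLS, resume at a reduced dose (Appendix F, Table 4).*
2. Limit the preceding no-reduction sentence to *chemical changes or laboratory TLS lasting < 48 hours*, so that the limit clearly covers both.

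If the sponsor's medical director prefers 72 hours, use that number and the same verb in both Section 6.2 and Appendix F. Leave Appendix D as it is.

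The cost is two sentences in a protocol amendment. Data collection, thresholds, the SAP and the sample size do not change. The clinical downside is a lower restart dose for some subjects who would otherwise have resumed at the same dose. Section 6.2 already allows re-escalation after a risk assessment and discussion with the medical director.

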5.4 Prior and Concomitant Therapy

Any medication or vaccine (including over-the-counter or prescription medicines, vitamins, and/or herbal supplements) that the subject is receiving at the time of enrollment or receives during the study must be recorded through the post-treatment visit (30-day follow-up visit) (refer to the Operations Manual Section 3.6).

Short courses (≤ 14 days) of steroid treatment for noncancer-related medical reasons (e.g., joint inflammation, asthma exacerbation, rash, antiemetic use, and infusion reactions) at doses that are clinically indicated are permitted.

Any questions regarding concomitant or prior therapy should be raised to the AbbVie emergency contact.

The following medications are allowed to use with caution **after** completion of the venetoclax dose ramp-up if no appropriate therapeutic alternative exists (additional guidance noted):

- strong CYP3A inhibitors (dose reductions for both venetoclax and ibrutinib)

The following **cautionary** medications include (if necessary, additional guidance noted):

- moderate CYP3A inhibitors (requires venetoclax and ibrutinib dose reductions)
- strong and moderate CYP3A inducers (avoid)
- P-glycoprotein (P-gp) substrates
- breast cancer resistance protein substrates/inhibitors
- organic anion-transporting polypeptide (OATP)1B1/1B3 substrates
- P-gp inhibitors

- supplements such as fish oil and vitamin E
- other anticoagulants or medications that inhibit platelet function (warfarin and coumarin derivatives prohibited)

Co-administration of a strong or moderate CYP3A inhibitor requires a specified venetoclax and ibrutinib dose adjustment as presented in [Table 1](#). After discussion with the investigator and AbbVie Therapeutic Area Medical Director (TA MD), co-administration of a strong CYP3A inhibitor with ibrutinib may be allowed.

Table 1. Dose Modifications for Venetoclax and Ibrutinib: Moderate and Strong CYP3A Inhibitor Use

Drug	Dose if No Moderate or Strong CYP3A Inhibitor	Dose if Co-Administered with a Moderate CYP3A Inhibitor	Dose if Co-Administered with a Strong CYP3A Inhibitor ^a
Venetoclax	20 mg	10 mg	-- ^b
	50 mg	20 mg	-- ^b
	100 mg	50 mg	-- ^b
	200 mg	100 mg	-- ^b
	400 mg	200 mg	100 mg
	600 mg	300 mg	150 mg
Ibrutinib	420 mg	140 mg	Withhold for duration of inhibitor use or reduce to 140 mg

CYP = cytochrome P450

a. Further dose reductions may be required.

b. Strong CYP3A inhibitors are prohibited during initial ramp-up.

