Management of treatment-emergent infections is the responsibility of the investigator. Institutional infectious organisms and their drug resistance patterns should primarily be considered and the choice of agents to treat these infections should be based on regional guidelines or institutional standards. The investigator should confirm that a concomitant medication/supplement can be safely administered with study drugs. Some medications may require dose adjustments due to the potential for drug-drug interactions. Refer to [Table 4](#) and [Table 5](#) for implementing dose modifications for venetoclax + ibrutinib as necessary.

Management of Major Hemorrhage

Fatal bleeding events have occurred in subjects treated with ibrutinib. For all hemorrhagic AEs, a transfusion of red blood cells may be required and ibrutinib may be withheld and/or reductions may be required.

Guidelines for Management with Antiplatelet Agents and Anticoagulants

Warfarin or vitamin K antagonists should not be administered concomitantly with ibrutinib. Supplements such as fish oil and vitamin E preparations should be avoided. Use ibrutinib with caution in subjects requiring other anticoagulants or medications that inhibit platelet function. Subjects with congenital bleeding diathesis have not been studied. Subjects requiring the initiation of therapeutic anticoagulation therapy (e.g., atrial fibrillation) should consider the risks and benefits of continuing ibrutinib treatment. If therapeutic anticoagulation is clinically indicated, treatment with ibrutinib should be held and not be restarted until the subject is clinically stable and has no signs of bleeding. Subjects should be observed closely for signs and symptoms of bleeding. No dose reduction is required when study drug is restarted.

In a drug-drug interaction study in healthy subjects, administration of a single dose of venetoclax with warfarin resulted in an 18% to 28% increase in observed maximum concentration (C_{max}) and area under the concentration versus time curve from time 0 to infinite time ($\text{AUC}_{0-\text{inf}}$) of R-warfarin and S-warfarin. Because venetoclax was not dosed to steady state, the international normalized ratio is recommended to be monitored closely in subjects receiving warfarin.

Guidelines for Ibrutinib Management with Surgeries or Procedures

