Venetoclax may cause a decrease in spermatogenesis. Male subjects considering preservation of fertility should bank sperm before initiating treatment with venetoclax.

Dose Modifications Based on Toxicities

Subjects who discontinue 1 study drug because of study drug-related toxicities may continue to receive the other study drug per the discretion of the investigator.

Dose Interruptions and Modifications for Venetoclax

See [Appendix F](#) for dose modifications for toxicities related to venetoclax and [Table 4](#) for recommendations for re-initiating venetoclax treatment after interruption. If venetoclax dose interruption is > 4 weeks, the TA MD should be consulted.

Dose modifications for possible drug-drug interactions are provided in [Section 5.4](#).

Table 4. Dose Modification for Toxicity During Venetoclax Treatment

Dose at Interruption (mg/day)	Restart Dose (mg/day) ^a
600	400
400	300
300	200
200	100
100	50
50	20
20	10

a. If patient is not hospitalized for close monitoring, continue the reduced dose for 1 week before increasing the dose.

Dose Interruptions and Modifications for Ibrutinib

Treatment with ibrutinib should be temporarily stopped for unmanageable, potentially ibrutinib-related toxicity that is Grade ≥ 3 in severity. Ibrutinib may be temporarily stopped for a maximum of 28 consecutive days. Ibrutinib should be discontinued permanently in the event of a toxicity lasting more than 28 days unless continued treatment is approved by the sponsor.

The dose of ibrutinib must be modified according to the dose modification guidance in [Table 5](#) and [Appendix F](#) if any of the following potentially drug-related toxicities occur:

- Grade 3 or higher neutropenia with infection or fever
- ANC < 500/ μ L
- platelets < 50,000/ μ L in the presence of clinically significant bleeding (Grade ≥ 2)
- platelets < 25,000/ μ L
- Grade 3 nausea or Grade 3 or 4 vomiting or diarrhea if persistent despite optimal antiemetic or antidiarrheal therapy
- any other Grade 4 or unmanageable Grade 3 toxicity

If the dose of ibrutinib is reduced, the dose of ibrutinib may be re-escalated at the investigator's discretion in the absence of a recurrence of the toxicity that led to the reduction. No dose escalation of ibrutinib above 420 mg is allowed in this study. Dose changes must be recorded in the dose administration eCRF.

Table 5. Ibrutinib Dose Reduction Levels

Starting Dose Level	420 mg
Dose reduction Level 1	280 mg
Dose reduction Level 2	140 mg

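### Two infection paragraphs in Protocol Section 6.2 follow a drug-interaction warning with a pointer to toxicity tables, while Section 5.4 and other lines of 6.2 put interaction dosing in Table 1; the two routes give different maintenance doses

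*Protocol*

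**What the plan says.** Two consecutive topics in Protocol Section 6.2, Prophylaxis for Infection and Management of Infection, share the same closing sequence. The investigator is to confirm that the agent can be given safely with study drugs. Then comes "Some medications may require dose adjustments due to the potential for drug-drug interactions. Refer to [Table 4](#) and [Table 5](#) for implementing dose modifications" of both drugs. Neither paragraph mentions Table 1 or Section 5.4.

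Table 4 is titled as a dose modification for toxicity. Its two columns are the venetoclax dose at interruption and the restart dose. Table 5 lists ibrutinib dose reduction levels. Neither has an entry for a concomitant inhibitor.

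Elsewhere the protocol gives a different route for interactions:

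- Section 5.4: "Co-administration of a strong or moderate CYP3A inhibitor requires a specified venetoclax and ibrutinib dose adjustment as presented in" Table 1.
- Section 6.2, venetoclax dose interruptions and modifications: "Dose modifications for possible drug-drug interactions are provided in" Section 5.4.
- Section 6.2, text after Table 5: "For dose modification during concomitant treatment with CYP3A inhibitors, refer to" Table 1.
- Operations Manual Section 3.6: dose reductions of both drugs are required with a strong or moderate CYP3A inhibitor, with Section 5.4 as the reference.

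**The concern.** In both infection paragraphs, interaction is the only stated reason for adjusting a dose, and the next sentence names the tables to use. A site that follows the paragraph it is reading would look up an interaction dose in tables built for another purpose. A site that starts from Section 5.4 would use Table 1. Two sites could then give the same subject different doses of both drugs, and no sentence says which instruction governs.

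The subjects concerned have severe neutropenia or an infection, so the matter is first one of safety. It also bears on how uniformly the regimen is given in a single-arm trial, although the documents offer no basis for putting a size on any effect on the response rate.

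**Working it through.** The plan states no figure to reproduce. The check sets the two routes side by side for the same starting dose.

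**Inputs.** Venetoclax restart doses come from Table 4 and the first ibrutinib reduction step from Table 5 (both Section 6.2). Interaction doses come from Table 1 (Section 5.4); for example, its 400 mg row reads "400 mg 200 mg 100 mg" for no inhibitor, moderate inhibitor and strong inhibitor.

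**Formula.** Ratio = dose from Table 4 or 5 ÷ dose from Table 1.

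| Starting dose (mg) | Table 4 or 5 | Table 1, moderate | Ratio | Table 1, strong | Ratio |
|---|---|---|---|---|---|
| Venetoclax 20 | 10 | 10 | 10/10 = 1.00 | prohibited in ramp-up | n/a |
| Venetoclax 50 | 20 | 20 | 20/20 = 1.00 | prohibited in ramp-up | n/a |
| Venetoclax 100 | 50 | 50 | 50/50 = 1.00 | prohibited in ramp-up | n/a |
| Venetoclax 200 | 100 | 100 | 100/100 = 1.00 | prohibited in ramp-up | n/a |
| Venetoclax 400 | 300 | 200 | 300/200 = 1.50 | 100 | 300/100 = 3.00 |
| Venetoclax 600 | 400 | 300 | 400/300 = 1.33 | 150 | 400/150 = 2.67 |
| Ibrutinib 420 | 280 (Level 1) | 140 | 280/140 = 2.00 | 140 or withhold | 2.00, or no finite ratio |

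For a moderate inhibitor the venetoclax routes agree up to 200 mg and part at 400 and 600 mg, the doses in use from Day 5 onward. The ibrutinib gap exists at the starting dose and closes at Table 5 Level 2, which is also 140 mg. Table 4 has a 300 mg level with no row in Table 1, so that level cannot be compared.

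**Can the diverging cells be reached?** Section 5.4 allows strong inhibitors with caution after ramp-up when no appropriate alternative exists, so the strong-inhibitor cells at 400 and 600 mg can apply. Operations Manual Appendix B lists anti-infectives in both classes: clarithromycin, itraconazole, ketoconazole, posaconazole and voriconazole as strong; ciprofloxacin, erythromycin, fluconazole and isavuconazole as moderate. The agents named as examples under Prophylaxis for Infection (acyclovir, zelitrex, trimethoprim-sulfamethoxazole, levofloxacin, amoxicillin-clavulanate) are not on those CYP3A inhibitor lists. The listed inhibitors enter because the prophylaxis text admits comparable agents and local standards, and because Management of Infection leaves the choice to local standards and is not tied to a neutrophil count.

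**The case against.** The strongest reply is that the pointer concerns toxicity. Prophylaxis is required when the neutrophil count falls below 500/µL. Where potentially drug-related, that count is itself a listed trigger for modifying ibrutinib under Table 5 and Appendix F. Appendix F also has venetoclax interrupted for Grade 4 hematologic toxicity, with Table 4 applying from the second occurrence. Tables 4 and 5 are thus the protocol's own tables for the event that prompts prophylaxis. This stands. A reader might infer that no study-drug toxicity is in play in the prophylaxis paragraph, so that the pointer can only mean interaction dosing; the documents do not support that. But the reply does not remove the ambiguity. The pointer directly follows the interaction sentence, and the infection-treatment paragraph repeats it without any neutropenia condition.

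A second reply is that a site turning to Tables 4 and 5 finds the other route beside them: the reference to Section 5.4 stands shortly before Table 4, and the reference to Table 1 follows Table 5. Table 4's title and columns also signal that it is not an interaction table. This stands as mitigation and makes a literal misreading less likely. It also means that Section 6.2 contains both instructions without ranking them.

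A third reply is that the large ratios are corner cases. Strong inhibitors are barred during ramp-up and later restricted to cases without an alternative, and giving one with ibrutinib calls for discussion with the sponsor's medical director. This stands: 3.00 is a maximum, not a typical value.

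**Conclusion.** The inconsistency is real and internal to the protocol. Two paragraphs read as sending interaction dosing to Tables 4 and 5, while Section 5.4, Operations Manual Section 3.6 and two other lines of Section 6.2 send it to Section 5.4 or Table 1. Read literally, the routes differ by a factor of 1.33 to 1.50 for venetoclax 400 or 600 mg with a moderate inhibitor, 2.67 to 3.00 with a strong inhibitor after ramp-up, and 2.00 or more for ibrutinib 420 mg. They do not differ for venetoclax 20 to 200 mg with a moderate inhibitor.

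These sizes assume that a site takes the pointer as the interaction route, reads one row of Table 4, takes the first step of Table 5, and uses an anti-infective that the protocol classes as a moderate or strong CYP3A inhibitor.

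Two stronger readings do not follow. One is that subjects will receive three times the Table 1 dose; that is a single cell of the comparison, and the Table 1 route is stated close to both tables. The other is that mandatory prophylaxis exposes every subject with severe neutropenia to the gap; the named prophylactic agents are not on the inhibitor lists. What is shown is a risk of conflicting instructions. No view is taken on which doses should apply.

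**What to change.** Reconcile the Prophylaxis for Infection and Management of Infection paragraphs with Section 5.4 and Table 1, Operations Manual Section 3.6, and the two interaction references elsewhere in Section 6.2, so that interaction dosing has one stated source. If Tables 4 and 5 are meant only for toxicity attributed to study drug, say so in a sentence separate from the interaction sentence. The sponsor decides which doses apply.

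The cost is two cross-references in a protocol amendment or administrative clarification. No new data, subjects or analyses are needed.
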